### 3.4 Protocol Deviations and Unanticipated Problems

Any protocol deviations or unanticipated problems will be listed by intervention group and summary statistics such as frequencies and percentages will be included if appropriate. The corresponding listings and descriptive summaries are outlined in Appendix A, Section A.4.

### 3.5 Primary and Secondary Outcomes

The analytic plan will examine the effect of the intervention by comparing data collected from 410 NH residents with advanced dementia (N=205/arm) in 28 NHs (14/arm) in the intervention vs. control arms. The primary outcome is the number or antimicrobial courses for suspected UTIs and LRIs/person-year over 12 months (Aim 1). Secondary outcomes are: antimicrobial courses for suspected UTIs and LRIs when minimal criteria for initiation are absent/person-year (Aim 2); advance care planning for infection management (Aim 3, H3a), and burdensome procedures/person-days to evaluate suspected LRIs and UTIs (Aim 3, H3b).

Descriptive analyses will include frequencies for categorical variables and means/medians with SDs/interquartile ranges for continuous variables. Outcomes will be compared between arms using negative binomial-logit hurdle regression models (H1, H2, and H3b) and Cox proportional hazards regression (H3a), with robust estimates of variance to account for clustering within NHs. All analyses will be at the resident level and follow intention to treat principles. The primary analysis will include intervention and the two variables we sought to balance with constrained randomization, for-profit status of the NH and resident race. Sensitivity analyses will adjust for imbalances in resident features, as needed. While we do not anticipate an effect on mortality, analyses will account for the competing risk of death and differential follow-up time due to mortality. Analyses will be done with SAS (SAS Institute, Inc., Cary, NC), Stata (College Station, TX), and R (R Foundation for Statistical Computing, Vienna).

# Aim 1: Compare antimicrobial courses for suspected UTIs and LRIs/person-years (primary outcome).

For H1, the number of antimicrobial courses for suspected UTIs and LRIs/person-years over 12 months will be compared between the study arms using negative binomial-logit hurdle regression models. This approach accommodates a potential excess of residents not receiving antimicrobials by using a two-stage process: a logit model examining the probability of receiving a least one antimicrobial course, and among those receiving at least one course, a truncated negative binomial model examining the number of courses. Length of follow-up (time to death, dropout, or study completion) will be included as an offset. Analyses will be at the resident-level. All residents contribute data for this analysis. A resident who experiences one or more suspected infections will have their number of antimicrobial courses associated with these episodes summed as the outcome, with the length of follow-up as the offset. A resident who experiences **no** suspected infections, will have 0 antimicrobial courses as the outcome, with the length of follow-up as the offset. Robust estimates of variance will account for clustering within

NHs. The logit portion of the model will generate ORs and the negative binomial portion will generate rate ratios (RRs), both with 95% Cls. A two-sided likelihood ratio test will jointly test whether the intervention reduces the probability of having at least one antimicrobial course, and given any antimicrobial use, the number of courses.

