### 1.2 Objectives and Outcomes

The Specific Aims are:

Aim 1. To conduct a cluster RCT of an intervention to improve infection management among 410 residents with advanced dementia (N=205/arm) residing in 28 NHs (N=14/arm) and compare the total number of antimicrobial courses for suspected UTIs and LRIs/person-year (primary outcome) over 12 months in the intervention vs. control (usual care) arms. Data will be obtained from review of the residents' charts and medication administration records q2months up to 12 months.

H1. The number of antimicrobial courses/person-years will be lower in the intervention vs. control arms.

Aim 2. To compare the number of antimicrobial courses prescribed for suspected UTIs and LRIs when minimal criteria for treatment initiation are absent based on consensus guidelines/person-vear (secondary outcome) in the intervention vs. control arm over 12 months.

H2. The number of courses prescribed when minimal criteria are absent /person-year will be lower in the intervention vs. control arm.

Aim 3. To compare the following outcomes in the intervention vs. controls arms over 12 months: i. advance care planning about infection management (e.g., documented discussions between proxies and providers, advance directives to withhold antimicrobials), and ii. number of burdensome procedures used to evaluate suspected LRIs and UTIs (hospital transfer, bladder catheterization, chest x-ray, blood draws)/person-year.

H3a. Advance care planning about infections will be higher in the intervention vs. control arms. H3b. The number of burdensome procedures/person-days will be lower in the intervention vs. control arms.

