### 1.8 Rationale for Number of Residents

Calculations use two-sided testing, assuming a type I error rate of 5% and 90% power, and adjust for potential dependence of observations within NHs using an intracluster correlation of 0.01 based on data from the Study of Pathogen Resistance and Exposure to Antibiotics in Dementia (SPREAD) study conducted in 35 NHs. Based on SPREAD data, we estimate the total antimicrobial courses/person-year in the control arm will be  $\sim$ 1.26, of which 72% (0.91 courses/person-year) will not meet minimal criteria for treatment. Based on prior work, we estimate that we can reduce the % of courses not meeting minimal criteria in the intervention arm by 35%, for a reduction in total courses of 25% (0.72 X 0.35=0.25). We anticipate another 5% reduction in total courses by decisions to withhold antimicrobials in the intervention arm, for total reduction of 30% (25% + 5% = 30%), resulting in an absolute reduction of 0.38 (0.30 X 1.26=0.38) in total courses/person years in the intervention vs. control arms.

Sample size estimates were computed using an approach for comparing rates based on a simplified assumption of a Poisson distribution for the number of antimicrobial courses. To achieve at least 90% power in testing for an absolute reduction in antimicrobial courses/person year of 0.38, we require a total of 28 NHs (14 NHs/arm), assuming each NH contributes, on average, 15 residents (total 410 residents; 205/arm) and each resident contributes, on average, 0.79 person-years based on SPREAD data. With this sample size, repeated power calculations for H1 using a more complex simulation of the negative binomial-logit hurdle model found that we will have > 90% for testing the joint effect of the intervention reducing the probability of having at least one antimicrobial course, and given any antimicrobial use, the number of courses. The sample size also provides adequate power to detect meaningful effect sizes for Aims 2 and 3. Control rates are based on prior studies; ~13% of residents will have advance care planning for infection management (documented provider-proxy discussions or new

directives to withhold antimicrobials) and experience 3.25 burdensome procedures/person-year for UTIs and LRIs.

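### The primary analysis gives no estimate with a confidence interval for total courses per person-year, and no reading of H1 when the two hurdle parts point in opposite directions

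*SAP*

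**What the plan says.** The target is one overall, directional quantity. H1 in SAP section 1.2 reads "The number of antimicrobial courses/person-years will be lower in the intervention vs. control arms". SAP section 3.5 says "The primary outcome is the number or antimicrobial courses for suspected UTIs and LRIs/person-year over 12 months (Aim 1"). SAP section 1.8 sizes the trial on the same scale, "resulting in an absolute reduction of 0.38 (0.30 X 1.26=0.38) in total courses/person years". Protocol section 9.2 explains that courses per person-year was chosen because it best reflects the aim of fewer antimicrobial starts.

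The analysis in SAP section 3.5, Aim 1, is a negative binomial-logit hurdle model with follow-up as offset. Its effect measures are: "The logit portion of the model will generate ORs and the negative binomial portion will generate rate ratios (RRs"), each with a 95% CI. The rate ratio (RR) comes from the truncated count part, so it describes residents with at least one course. The test is joint: "A two-sided likelihood ratio test will jointly test whether the intervention reduces the probability of having at least one antimicrobial course" and, given any use, the number of courses.

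Elsewhere, section 3.5 adds general descriptives ("Descriptive analyses will include frequencies for categorical variables and means/medians with SDs/interquartile ranges for continuous variables"), covariates and robust variance. Section 3.6 adds missing-data, any-reason, UTI/LRI-separate and by-procedure analyses. The Appendix A shells contain no outcome table. Protocol section 13 defers to the SAP. Aim 2 (H2) and the burdensome-procedure part of Aim 3 (H3b) adopt the Aim 1 approach.

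**The concern.** In a hurdle model the overall rate is the product of two things: the probability of any course, and the mean number of courses among users. Neither the odds ratio (OR) nor the count-part RR is the ratio of overall rates. A two-sided test on 2 degrees of freedom has no sign: it rejects for an OR below 1 with an RR above 1 as readily as for two reductions.

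If the parts disagree, a significant primary test would not show whether total use fell. The summary used to settle that question would be chosen after seeing the data. Even when the parts agree, no planned estimate with a CI can be set beside the 0.38 reduction on which the trial was sized. H2 and H3b share the gap.

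**Working it through.** **1. The plan's own figure.** Inputs from SAP 1.8: control rate 1.26, ratio 0.70, 0.79 person-years per resident, two-sided 5%, 90% power, intracluster correlation 0.01, 15 residents per home. A Poisson-regression formula with null variance gives

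N = [1.96·√4 + 1.2816·√(2 + 2/0.70)]² / [0.79 × 1.26 × (ln 0.70)²] = 359.2.

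Times the design effect 1 + 14 × 0.01 = 1.14, this is 409.5, i.e. 410. The sample size reproduces, and it is built on the overall rate.

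**2. What the missing estimate would look like at the planning values.** Design effect 1 + (410/28 − 1) × 0.01 = 1.136. Effective person-years per arm 205 × 0.79 / 1.136 = 142.5. With Poisson variance:
- SE of log RR = √[(1/1.26 + 1/0.882)/142.5] = 0.116, so RR 0.70 (95% CI 0.56 to 0.88).
- SE of the difference = √[(1.26 + 0.882)/142.5] = 0.123, so −0.38 (−0.62 to −0.14) courses per person-year.

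**3. Can the joint test reject when total use is unchanged?** Mean courses per resident is 1.26 × 0.79 = 0.995 in both arms. Any-use and dispersion are assumptions, because the documents give neither. If any-use falls from 30% to 24%, users must average 0.995/0.24 = 4.15 courses instead of 0.995/0.30 = 3.32, which is 25% more. The count-part mean m solves m / [1 − (1 + αm)^(−1/α)] = mean among users, where α is the dispersion.

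Rejection is P(χ²₂(λ) > 5.991), with λ the sum of the logit and count contributions divided by 1.136. Two worked cases:
- 30% to 24%, α = 1.0: logit part 205 × 0.06² / (2 × 0.27 × 0.73) = 1.87; count part, computed numerically, 1.86; λ = 3.73/1.136 = 3.28; rejection 35%.
- 45% to 36%, α = 0.3: logit part 205 × 0.09² / (2 × 0.405 × 0.595) = 3.45; count part 4.79; λ = 8.24/1.136 = 7.25; rejection 67%.

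| Control any-use | Relative drop | OR | Count RR (α 0.3 to 1.0) | Rejection (α 0.3 / 0.5 / 1.0) |
|---|---|---|---|---|
| 30% | 20% | 0.74 | 1.32 to 1.36 | 0.448 / 0.402 / 0.349 |
| 45% | 20% | 0.69 | 1.40 to 1.46 | 0.674 / 0.637 / 0.587 |
| 30% | 10% | 0.86 | 1.14 to 1.16 | 0.137 / 0.126 / 0.115 |
| 45% | 10% | 0.83 | 1.18 to 1.20 | 0.204 / 0.193 / 0.178 |

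**4. Simulation with clustering.** 2,000 trials per case; 28 homes, 410 residents, 40% deaths by 12 months, follow-up offset, two covariates, α = 0.3. The overall CI is for the standardised rate ratio, cluster-robust with a t reference on 26 df. The rule is the one set out under the fix.

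| Case | Joint test significant | Overall CI below 1 | Rule supports H1 | OR and RR discordant |
|---|---|---|---|---|
| Equal rates, any-use 30% to 24% | 49.8% | 3.4% | 3.4% | 86.9% |
| Equal rates, any-use 45% to 36% | 72.4% | 3.2% | 3.2% | 94.4% |
| Both parts fall, total 30% lower | 86.1% | 87.8% | 85.0% | 3.8% |
| Only any-use falls, total 30% lower | 94.3% | 78.2% | 78.2% | 51.1% |
| Single-course users removed, total 12% lower | 71.7% | 18.3% | 18.4% | 86.6% |

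**The case against.** The strongest defence is that the plan works for the effect it expects. SAP 1.8 builds the 30% reduction by removing courses: 25% through minimal criteria and 5% through withholding. If each course is removed independently with probability 0.30 (assuming structural non-users plus negative binomial counts, dispersion 0.3), the count RR is 0.70 and the OR is 0.87, 0.76 or 0.70 at control any-use of 30%, 45% or 52%. Both parts fall, so the overall rate falls. The Aim 1 text also words the test in terms of reduction, both partial effects carry CIs, and crude arm rates could be tabulated. This stands, and it limits the size of the point. It does not close the gap: the wording gives a two-sided joint test no direction, and a crude rate without a planned CI or reading does not settle H1.

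The equal-rate cases are also demanding. With a 20% drop in any-use they need a count RR of about 1.3–1.5, and nothing in the documents suggests the programme would raise courses per user that much. They show what the test permits, not what is likely.

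A reader might infer two stronger things that the documents do not support.
- That discordance is common because about half of trials show it when only any-use falls. There the true RR is 1.00, so its estimate lands on either side of 1 by chance; the same happens under a full null (52%).
- That false support could reach 71–93%, using the 52–66% in Protocol 5.1.1 as control any-use. That range covers any antimicrobial, not courses for suspected UTIs and LRIs. At a mean of 0.995 courses, a plain negative binomial with dispersion 0.3 already gives 58% any-use, so 60–66% means fewer zeros than that, whereas the SAP chose the hurdle for a possible excess of zeros.

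**Conclusion.** The point holds in a limited form and should be addressed. The plan has no estimate with a CI of the quantity named in H1, and no reading when the two parts disagree. As written, it could give a significant primary test with no change in total use: about 35–67% of trials for a 20% relative drop in any-use at equal overall rates and control any-use 30–45%, and about 12–20% for a 10% drop. These figures rest on assumed any-use and dispersion (0.3–1.0) and are illustrations only.

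If the intervention lowers both parts, the gap matters little: about 4% of trials are discordant, and the rule supports H1 in 85% against 86% for the joint test. It would be wrong to infer that the hurdle model is unsuitable or that 410 residents is miscalculated on this account. The model is reasonable and the figure reproduces.

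**What to change.** Keep the hurdle model, the joint test, the OR and the RR. In SAP section 3.5, Aim 1:

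1. Name as the key effect estimate for H1 the overall rate ratio and rate difference in courses per person-year. Predict every resident's courses under each arm from the fitted hurdle model, with the same covariates and follow-up, and divide total predicted courses by total person-years.
2. Give a cluster-robust 95% CI with a small-sample correction for 28 homes. In the equal-rate simulations above, a t reference alone left 3.2–3.4% of intervals wrongly below 1, against a nominal 2.5%.
3. State one rule. A significant joint test supports H1 if both parts favour the intervention. If the parts are discordant, a significant joint test supports H1 only if the 95% CI for the overall rate ratio lies below 1.
4. Apply the same to H2 and H3b.

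The cost is one standardisation step and SAP wording; no new data are needed. The rule is stricter than the joint test when only one part improves: 78% against 94% if only any-use falls and total use is 30% lower, and 18% against 72% if only single-course users are removed and total use is 12% lower. SAP 1.8 says "we will have > 90% for testing the joint effect of the intervention reducing the probability of having at least one antimicrobial course" and, given use, the number of courses. That figure should be described as applying to the joint test only, and power under the adopted rule should be stated beside it.

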# Aim 2: Compare total antimicrobial courses for suspected UTIs and LRIs when minimal criteria for initiation are absent/person-years (secondary outcome).

For H2, total antimicrobial courses for suspected UTIs and LRIs when minimal criteria for initiation are absent/person-years over 12 months will be compared between the intervention and control arms. As in our prior studies, the determination that a treated episode did not meet minimal criteria will be based on consensus guidelines using signs and symptoms documented in the residents' charts. The analytic approach to H2 will be the same as that described for H1. All residents contribute data for this analysis. A resident who experiences one or more suspected infections when minimal criteria for initiation were absent will have their number of antimicrobial courses associated with these episodes summed as the outcome, with the length of follow-up as the offset. A resident who experiences **no** suspected infections when minimal criteria for initiation were absent, will have 0 antimicrobial courses as the outcome, with the length of follow-up as the offset.

# Aim 3: Compare: i. advance care planning and ii. use of burdensome procedures (secondary outcomes).

For H3a, the analysis will compare advance care planning for infections over 12 months defined as having no advance directives to withhold antimicrobials and acquiring a new advance directive to withhold antimicrobials by any route (oral, intramuscular, or intravenous) or having a less restrictive directive to withhold antimicrobials and acquiring a more restrictive directive to withhold antimicrobials. Residents with directives restricting all routes of antimicrobial use at baseline will be excluded. Time to the date of the new directive will be compared between arms using Cox proportional hazards regression modeling with a robust variance estimate to account for clustering at the NH level. Residents who die, dropout, or complete the study without these directives will be censored. HRs and 95% CIs will be generated. For H3b, the main analysis will compare the total number of burdensome procedures (bladder catheterizations, blood draws, chest x-rays, and hospital transfers) used to evaluate a suspected UTI or LRI/person-years between arms. The analytic approach will be same as described for H1.

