#### 7.3.3 Resident Enrollment

We have obtained an IRB waiver of individual authorization for disclosure of personal health information (PHI) to screen and identify eligible residents. At the start of the study and every 2 months for 12 months in each NH, the RA will interview unit nurses to identify eligible residents. Eligibility and proxy information will be confirmed by chart review. Within one week of eligibility screening, proxies of eligible residents in the intervention NHs will be mailed study information, including the infection management booklet and the project director's (PD's) contact information if they wish to opt out. In addition, flyers will be posted in ALL participating facilities (control and intervention) explaining that the study is being conducted and that it includes data collection from the charts of residents with advanced dementia. The flyers will include contact information for the PD to ask further questions and an opportunity for proxies to "opt-out". If proxies do not contact the PD within two weeks, the resident will be enrolled and included in bi-monthly chart review with data abstraction.

[figure not shown]
PHI will not be removed from the facility. For purposes of recording and tracking eligible residents, study IDs will be assigned to eligible residents at the point of eligibility screening. A code sheet containing the names associated with assigned study IDs will be stored in a secure location within the participating NH.

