##### **13.1.1 Residents:**

Data will be collected by a trained RAs masked to the aims, outcomes, and that there are 2 arms. All data will be obtained from the residents' charts except for functional status and proxy ability to communicate in English, which will be ascertained in a 1-minute nurse interview at baseline. Charts will be abstracted (~20 minutes) when residents are first enrolled (baseline), q2months, and within 30 days of death, for up to 12 months. REDcap will be used for collecting data electronically and tracking protocol elements.

All resident data will be entered and managed in HSL data systems under a confidential study ID. The code sheet linking study ID to individual resident will be kept in a secure location within the NH. HSL data bases will maintain data under subject study ID related to nursing home name, age, and gender. Access to this code sheet will be limited to the RA assigning the codes, the study site champion and the project manager as needed to facilitate mailing of booklets to proxies of enrolled residents.

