### 2.3 Definitions of Analysis Populations

Intent-to-Treat (ITT) Population:

All eligible residents enrolled into the study will be included in the ITT population. The ITT population will be the primary analysis population for all primary and secondary outcomes.

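### H3a fixes directive status at enrolment, when intervention-arm proxies may already have the booklet; use the eligibility-screening date in both arms instead

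*SAP*

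**What the plan says.** SAP 3.5 (Aim 3) counts as an H3a event a first directive to withhold antimicrobials by any route, or "having a less restrictive directive to withhold antimicrobials and acquiring a more restrictive directive to withhold antimicrobials". It then states: "Residents with directives restricting all routes of antimicrobial use at baseline will be excluded". The model is given as follows: "Time to the date of the new directive will be compared between arms using Cox proportional hazards regression modeling". No time origin is defined, and neither is the date on which baseline directive status is read.

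The protocol supplies the sequence. Section 7.3.3: "Within one week of eligibility screening, proxies of eligible residents in the intervention NHs will be mailed study information, including the infection management booklet". The same section continues: "If proxies do not contact the PD within two weeks, the resident will be enrolled and included in bi-monthly chart review with data abstraction". Section 13.1.1 equates baseline with enrolment: "Charts will be abstracted (~20 minutes) when residents are first enrolled (baseline". Section 9.2.2 makes baseline abstraction subject to the proxy not having asked for exclusion. Section 8.5.8 repeats that the booklet goes out within a week of each screening.

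Other passages are looser. Sections 2.6 and 8, and one sentence of 8.2, place the booklet at resident enrolment, while a later sentence of 8.2 says it follows screening. Control homes receive flyers and usual care, with no booklet and no training.

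On the analysis set, SAP 2.3 says: "The ITT population will be the primary analysis population for all primary and secondary outcomes".

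**The concern.** The booklet is meant to prompt proxies to raise infection management with providers, which is how a new directive arises. If directive status is read after the mailing, the first directives it prompts fall before the clock starts. An all-route directive takes the resident out of the H3a analysis. A partial directive becomes the starting state, so it is not an event and only a stricter one will count.

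Background directives in the same weeks are treated this way in both arms. The excess prompted by the booklet arises in the intervention arm alone. The analysed set and the event definition therefore depend on something measured after randomization that the intervention is designed to change, and the expected direction is toward no effect. The only sensitivity analysis specific to H3a in SAP 3.6 is Fine-Gray for death, which does not address this.

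**Working it through.** **Order of events, intervention home (Protocol 7.3.3, 8.5.8, 9.2.2, 13.1.1).** Screening; booklet mailed within 1 week; two-week opt-out window, start not stated; enrolment and baseline abstraction.

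**Length of the gap from mailing to baseline.**
- Window counted from screening, mailing on day 7: 14 − 7 = 7 days, about 1 week.
- Window counted from mailing: 2 weeks.
- Baseline review a further week later: 3 weeks.
- Booklet sent at enrolment (the looser passages): no gap.

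**No plan figure to reproduce.** SAP 1.8 calls power for Aims 2 and 3 adequate but gives no number and no effect size for H3a. What follows is an illustration.

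**Inputs.** From SAP 1.8: 205 per arm, 28 homes, intracluster correlation 0.01, two-sided 5%, control proportion 13%. Assumed: intervention proportion 26.4%, chosen to give 90% power; directives spread evenly over 52 weeks; a two-proportion test in place of the Cox model; deaths ignored.

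- Design effect = 1 + (410/28 − 1) × 0.01 = 1.136.
- Effective n per arm = 205 / 1.136 = 180.4.
- Power = Φ(d / SE − 1.96), with d = pI − pC and SE = √{[pC(1 − pC) + pI(1 − pI)] / 180.4}.
- No gap: d = 0.134, SE = 0.0413, d/SE = 3.246, power = Φ(1.286) = 90%.

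The share of a year's directives in a gap of w weeks is w/52. Intervention points lost are 26.4 × w/52, and residents lost are 205 × 0.264 × w/52.

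| Gap | Share | Points lost | Residents | pI left | d/SE | Power, loss in intervention arm only | Power, same share lost in both arms |
|---|---|---|---|---|---|---|---|
| 1 week | 1.9% | 0.51 | 1.0 | 25.9% | 3.135 | 88.0% | 89.4% |
| 2 weeks | 3.8% | 1.02 | 2.1 | 25.4% | 3.024 | 85.6% | 88.6% |
| 3 weeks | 5.8% | 1.52 | 3.1 | 24.9% | 2.912 | 83.0% | 87.8% |

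The last column also takes the share from the control arm (13% becomes 12.75%, 12.5% and 12.25%), because the baseline cut applies there as well.

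The table treats the directive as an uncounted event (partial route). If the resident is excluded instead (all routes), pI becomes (pI − g)/(1 − g), where g is the proportion lost, and one-arm power is 88.5%, 86.7% and 84.7%. With a constant hazard in place of an even spread, the share is [1 − 0.736^(w/52)] / 0.264, that is 2.2%, 4.4% and 6.6%, and one-arm power for uncounted events is 87.7%, 84.8% and 81.6%.

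**Limit on the 13%.** SAP 1.8 defines that control rate as documented provider-proxy discussions or new directives. The H3a outcome in SAP 3.5 counts directives only, so the relevant control rate may be lower.

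**The case against.** A resident already restricted on all routes cannot have the event, so leaving that resident out of the risk set is natural. The SAP states the restriction openly, residents are still analysed by the arm of their home, and those with a partial directive stay in. SAP 3.2 and Table A.2.1 summarise baseline advance care planning by arm, which could show an imbalance, and SAP 3.6 examines imbalances in resident characteristics. A directive also takes time: the proxy must read the booklet, talk to a provider and obtain an order, and Protocol 8.5.2 points such talks to quarterly care-planning meetings. All of this stands, and it argues for a small effect. It does not supply a reference date before the mailing.

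Four stronger readings are tempting, and the documents do not carry them.

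- **Baseline is always at least two weeks after the booklet.** Section 7.3.3 does not say when the two weeks start, and Sections 2.6 and 8 and part of 8.2 place the booklet at enrolment.
- **The SAP contradicts its own intention-to-treat statement.** SAP 2.3 names the general population and SAP 3.5 adds an at-risk restriction for one outcome. The fair criticism is that the restriction uses a post-randomization variable and the SAP does not discuss this.
- **A large part of the H3a effect is lost.** That needs an early spike of directives after the mailing, for which the documents give no figure.
- **A screening-date origin cures the problem.** Staff training starts the intervention period (Protocol 8.4.2.4) and residents enter over the next 12 months (Protocol 8), so screening status may already reflect training.

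**Conclusion.** The point holds in a limited form. On Protocol 7.3.3 and 8.5.8, H3a directive status is read after the booklet has gone to one arm, and the SAP fixes no earlier date. The bias is toward no effect. For the booklet window it is probably modest: about 1 to 3 intervention residents, with power of roughly 83–88% where 90% was assumed, and nearer 88–89% if both arms lose the same share. These figures rest on an assumed 26.4% intervention proportion, an even spread of directives and a 13% control rate that covers more than the present outcome. An early response to the mailing would make the loss larger. If the booklet is in fact sent only at enrolment, the window closes and only the training exposure remains, whose size cannot be derived from the documents. The matter touches one secondary outcome and leaves the primary analysis alone. It is worth correcting because the bias is avoidable and the correction is cheap.

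**What to change.** In SAP 3.5, for H3a:

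1. Define directive status and Cox time zero at the eligibility-screening date, before the booklet is mailed, in both arms. Count directives dated after screening as events. Protocol 9.2 already collects the occurrence and date of advance care planning events.
2. Report by arm the number of residents excluded for all-route directives and the directive status at the reference date. Step 1 does not remove earlier staff training, and this shows whether the arms already differ.
3. Add a sensitivity analysis of all enrolled residents without the exclusion, on having a restrictive directive in place by the end of follow-up.

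Reconcile the protocol passages on booklet timing (2.6, 7.3.3, 8, 8.2, 8.5.8), and say from when the two-week opt-out period runs.

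The cost is SAP wording and a small date derivation, with no new data. There are two drawbacks. Moving time zero to screening adds a short interval in which every enrolled resident is alive by definition, since Protocol 7.2.3 excludes those who die before baseline; the rule is the same in both arms. The analysis without the exclusion is diluted by directives that predate the trial, so it supports the main H3a analysis and should not replace it.

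### With 28 homes and no small-sample correction, the cluster-robust Cox analysis of H3a has a type I error of about 6% to 8% and intervals that are too narrow

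*SAP*

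**What the plan says.** SAP 3.5 sets one approach to clustering for every outcome: regression models "with robust estimates of variance to account for clustering within NHs". Under Aim 3, H3a is time to a new or more restrictive directive to withhold antimicrobials, analysed by "Cox proportional hazards regression modeling with a robust variance estimate to account for clustering at the NH level", with hazard ratios and 95% CIs. No other test is named for H3a, so its p-value and its interval both rest on the robust variance.

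For H1, and for H2 and H3b by reference to it, the odds and rate ratios get 95% CIs with robust variance, but the hypothesis test is a joint likelihood ratio test.

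SAP 1.8 sets the nominal error and the clustering: "Calculations use two-sided testing, assuming a type I error rate of 5% and 90% power", with an "intracluster correlation of 0.01", 28 homes and 410 residents. SAP 3.5 lists three software packages. It does not say which version of the robust variance or which reference distribution will be used. SAP 3.6 adds a Fine-Gray sensitivity analysis for H3a and no small-sample method.

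**The concern.** The sandwich variance estimates the between-home variability of the score from 28 home totals. With that few totals it is too small on average, and it is itself noisy. Dividing by it and comparing with 1.96 ignores both problems. Uneven home sizes and home-level covariates, such as for-profit status, make the bias worse.

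At stake is a named secondary outcome. The H3a test would reject a true null more often than the stated 5%, and the hazard ratio interval would cover less than 95% of the time. H3a is a different model from the hurdle models, so settling the inference for those would leave it unchanged.

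**Working it through.** **1. The plan's own figure.** This checks that the inputs are read as intended. From SAP 1.8: control rate 1.26; "absolute reduction of 0.38 (0.30 X 1.26=0.38) in total courses/person years", so the rate ratio is 0.70; "each resident contributes, on average, 0.79 person-years based on SPREAD data"; average home size 15. With the sample-size formula for Poisson regression:

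N = [1.96·√4 + 1.2816·√(2 + 2/0.70)]² / [(ln 0.70)² × 1.26 × 0.79] = 359.2

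Design effect = 1 + (15 − 1) × 0.01 = 1.14, and 359.2 × 1.14 = 409.5, against 410 stated. The figure is reproduced. The SAP gives no operating characteristic for H3a.

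**2. Inputs for H3a.** 28 homes and 410 residents (410/28 = 14.6 per home); 13% incidence, so 0.13 × 410 ≈ 53 events under the null (SAP 1.8); 40% mortality (SAP 3.6); intracluster correlation 0.01. On the 13% scale this correlation means a squared coefficient of variation of home rates of 0.01 × 0.87/0.13 = 0.067.

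Assumptions not in the documents:
- home-size CV of 0, 0.5 or 0.8
- log-normal home effects
- exponential event and death times
- 18 of 28 homes for-profit, balanced by arm
- 12% of residents in the race category
- simple 1:1 allocation instead of minimization
- no residents excluded for baseline directives

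**3. A closed-form guide.** Suppose the robust variance behaves like a 26-df estimate shrunk by 26/28. The effective critical value is then 1.96 × √(26/28) = 1.889, and P(|t₂₆| > 1.889) = 7.0%.

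**4. Null simulation of the Cox model** (intracluster correlation 0.01; 20,000 runs per row; Monte Carlo SE about 0.2 points). The last column applies K/(K−2) with t on 26 df, or K/(K−3) with t on 25 df when covariates are included.

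| Size CV | Covariates | Mean robust SE | True SD of log HR | Shortfall | Uncorrected, 1.96 | Corrected |
|---|---|---|---|---|---|---|
| 0 | none | 0.281 | 0.299 | 6.0% | 6.7% | 4.7% |
| 0.5 | none | 0.283 | 0.302 | 6.3% | 7.0% | 5.0% |
| 0 | both | 0.277 | 0.301 | 8.0% | 7.4% | 4.7% |
| 0.5 | both | 0.279 | 0.308 | 9.4% | 7.9% | 5.3% |

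Shortfall = 1 − mean SE/true SD. K/(K−1) scaling alone leaves 6.2% to 7.4%. A t reference on 26 df alone leaves 5.5% to 6.6%.

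**5. Fewer events.** The 13% in SAP 1.8 counts documented discussions as well as directives. The H3a definition in 3.5 counts directives only and excludes residents already restricted on all routes. A separate simulation with clustering near 0.01 gave 6.6% to 8.0% at about 13% incidence and 6.1% to 7.1% at about 6.5%, with standard errors about 5% to 10% too small. Another, with gamma home effects and 4,000 runs per cell, gave 5.7% to 7.6% across incidences of about 6% and 12%.

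**6. Beyond the SAP's inputs** (4,000 to 5,000 runs per cell), uncorrected:
- CV 0.8 at 0.01: 8.4% to 8.5%
- correlation 0.03, CV 0.5, covariates: 8.3%
- correlation 0.05: 8.0% to 9.3%
- correlation 0.10: 8.5% to 11.1%

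With CV 0.8 or correlations of 0.05 to 0.10, the simple correction leaves about 5.5% to 7.3%.

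**7. Hurdle-model intervals** (correlation 0.01, adjusted, dispersion 1.0 assumed; 3,000 runs). Uncorrected robust tests of single coefficients, which mirror the CIs, reject in 7.9% to 8.4% (logit) and 7.7% to 9.2% (truncated negative binomial). The likelihood ratio test itself rejects in 5.9% to 7.1%.

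**The case against.** The strongest reply is that the excess is modest. On the SAP's own clustering it is one to three percentage points, for one secondary outcome, and at the lower event counts it can be nearer 6% than 8%. That is fair, and it limits the size of the point without removing it.

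A reader might infer two stronger claims that the documents do not support:

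- **That H3a runs at 8% to 9%.** This needs very uneven homes or a correlation several times 0.01. SAP 1.8 gives no figure for variation in home size. Its 0.01 is not specific to H3a, so a higher value is possible, but that is an assumption.
- **That all outcomes have inflated p-values from this cause.** The H1, H2 and H3b p-values come from a likelihood ratio test, which the sandwich does not enter. The excess of that test comes from ignoring clustering, which is a separate issue. Only the odds and rate ratio intervals share the present problem.

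It may also be said that the analyst could apply a correction without the SAP saying so. But the SAP leaves the choice open, and K/(K−1) scaling alone is not enough.

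Two reservations about the working stand. The simulations used simple allocation where SAP 1.5 plans minimization. Only the simple scaling with a t reference was tested, not the bias-corrected sandwiches or a bootstrap.

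**Conclusion.** The point holds for H3a. With 28 homes and an uncorrected robust variance, the standard error of the log hazard ratio is about 5% to 10% too small. A nominal 5% test rejects in about 6% to 8% of null trials, so the 95% interval covers about 92% to 94%. This rests on the SAP's correlation of 0.01, incidence of about 13% or lower, 40% mortality, assumed home-size CVs of 0 to 0.5, and a normal reference. Figures near 9% or above belong to clustering or size variation outside the plan.

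For the hurdle models, the conclusion extends to the robust odds and rate ratio intervals and no further. It does not cover the primary p-value.

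**What to change.** State in SAP 3.5 that all cluster-robust standard errors and CIs use a small-sample correction: the H3a Cox model, its Fine-Gray sensitivity analysis, and the hurdle odds and rate ratios. A bias-corrected sandwich (Kauermann-Carroll or Fay-Graubard) is preferable. K/(K−2) scaling is the minimum. Either should be paired with a t reference on homes minus home-level parameters, about 26 df unadjusted and 25 with for-profit status in the model.

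The cost is SAP wording and wider intervals. Under the simple scaling the log hazard ratio interval widens by a factor of 2.056 × √(28/26)/1.96 = 1.09 (26 df), or 2.060 × √(28/25)/1.96 = 1.11 (25 df, K/(K−3)). At correlation 0.01 with size CV up to 0.5 this brought H3a to 4.7% to 5.3%; the separate simulation in step 5 gave 3.9% to 5.9% with K/(K−2) and 26 df. Slight inflation may remain if the correlation is high or home sizes are very uneven, which is the reason to prefer the bias-corrected form.

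This change does not repair the likelihood ratio test, which needs its own decision. Replacing it with an uncorrected joint robust Wald test would not help: that test rejected in 10.7% to 11.7% of null runs at correlation 0.01.
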